11.4.3. Correlation Between Antiviral Effect and Clinical Course Endpoints

Selected antiviral effect and clinical course endpoints (parent[s]/caregiver[s] PRESORS and clinician PRESORS scores) will be subjected to correlation analysis. Various approaches, including graphical analysis, regression methods but also longitudinal analyses will be utilized.

More details regarding the analysis of these data will be described in the SAP.

11.4.4. Viral Sequencing

The sequencing results of the F-gene (and other regions of the RSV genome, if applicable, at the request of the protocol virologist) and changes from baseline will be summarized. Sequencing results may be presented in a separate report.

11.5. Safety Analyses

Safety data will be presented descriptively. Statistical testing of safety data, if appropriate, may be presented in a separate report.

For safety, baseline is defined as the last assessment prior to the first intake of study drug.

The population for the safety analysis will consist of all randomized subjects who received at least 1 dose of study drug.

Adverse Events

The verbatim terms used in the eCRF by investigators to identify AEs will be coded using the Medical Dictionary for Regulatory Activities (MedDRA). Treatment-emergent AEs are defined as AEs with onset during the treatment phase or that are a consequence of a pre-existing condition that has worsened since baseline. All reported AEs will be included in the analysis. For each AE, the percentage of subjects who experienced at least 1 occurrence of the given event will be summarized by treatment group.

Summaries, listings, datasets, or subject narratives may be provided, as appropriate, for those subjects who died, who discontinued treatment due to an AE, or who experienced a severe or a serious AE.

Clinical Laboratory Tests

Laboratory data will be summarized by type of laboratory test. Descriptive statistics will be calculated for each laboratory analyte at baseline and for observed values and changes from baseline at each scheduled timepoint. Changes from baseline results will be presented in pre-versus post-treatment cross-tabulations (with classes for below, within, and above normal ranges). Frequency tabulations of the abnormalities will be made. A listing of subjects with any laboratory results outside the reference ranges will be provided. A listing of subjects with any markedly abnormal laboratory result will also be provided.

The laboratory abnormalities will be determined per the criteria specified in the DMID (see [Attachment 1](#)) pediatric toxicity tables and in accordance with the normal ranges of the clinical laboratory if no gradings were available.

Results from the central laboratory will be included in summary tables. Local laboratory results (in case of cardiac events potentially related to QT prolongation) will be listed only.

Electrocardiogram (ECG)

The effects on cardiovascular variables will be evaluated by means of descriptive statistics and frequency tabulations. These tables will include observed values and changes from baseline values at each selected timepoint (the screening ECG will be used as baseline). Frequency tabulations of the abnormalities will be generated.

The ECG variables that will be presented are heart rate, PR interval, QRS interval, QT interval, QTcF, and QTcB.

The percentage of subjects with abnormalities will be tabulated.

Changes from baseline results will be presented in pre- versus post-treatment cross-tabulations (with classes for below, within, and above normal ranges).

Vital Signs

Descriptive statistics of body temperature, heart rate, respiratory rate, SBP, DBP, and SpO₂ values and changes from baseline will be summarized at each scheduled timepoint. The percentage of subjects with values beyond clinically relevant limits (as defined in the SAP) will be summarized.

Physical Examination

Physical examination findings will be summarized at each scheduled time point.

11.6. Pharmacokinetic Analyses

Population PK analysis of concentration-time data of JNJ-53718678 may be performed using nonlinear mixed-effects modeling. Data may be combined with those of other selected studies to support a relevant structural model. Available baseline subject characteristics (demographics, laboratory variables, race, etc.) will be tested as potential covariates affecting PK parameters. Details will be given in a population PK analysis plan and the results of the population PK analysis will be presented in a separate report.

A snapshot date for PK samples to be analyzed will be defined, if required. Samples collected before this date will be analyzed for JNJ-53718678 and included in the population PK analysis. Samples collected after the snapshot date will be analyzed at a later date, and may be included in a population PK re-analysis when they become available after database lock.

Data will be listed for all subjects with available whole blood concentrations per intervention group. Subjects will be excluded from the PK analysis if their data do not allow for accurate assessment of the PK (eg, incomplete administration of the study drug; missing information of dosing and sampling times; concentration data not sufficient for PK parameter calculation).

All concentrations below the lowest quantifiable concentration or missing data will be labeled as such in the concentration database. All subjects and samples excluded from the analysis will be clearly documented in the study report.

For each intervention group, descriptive statistics, including arithmetic mean, SD, coefficient of variation, median, minimum, and maximum will be calculated for all individual derived PK parameters including exposure information of JNJ-53718678, and, if applicable, of metabolites and/or endogenous markers.

11.7. Pharmacokinetic/Pharmacodynamic Relationships

Relationships of JNJ-53718678 population-derived exposure parameters with selected antiviral activity parameters, clinical outcomes, and safety endpoints will be explored. These relationships will be presented in a tabular and/or graphical display.

Results of PK/PD analyses may be presented in a separate report.

11.8. Medical Resource Utilization Analyses

Medical resource utilization will be descriptively summarized by treatment group.

11.9. Acceptability and Palatability

Data on acceptability and palatability of the JNJ-53718678 formulation will be presented descriptively.

11.10. Biomarker Analyses

Analyses may be performed at the sponsor's discretion and reported separately from this study. Statistical approaches to explore correlations between clinical outcome, viral load, and biomarkers in blood and mid-turbinate nasal swabs vary and depend on the different data types of the applied technology platforms, as well as on the extent of observed differences among study subjects.

11.11. Other Analyses

Data on viral (other than RSV) or bacterial pathogens (both by multiplex PCR) determined in mid-turbinate nasal swabs collected at screening will be listed.

11.12. Independent Data Monitoring Committee

An IDMC will be established to monitor and review data in an unblinded manner on a regular basis to ensure the continuing safety of the subjects enrolled in this study. The committee will meet periodically to review safety data, safety and PK data of the subcohort of Cohort 1 and results from interim analyses. In addition, an IDMC analysis of the safety and PK data of the full cohort of hospitalized subjects (including the full subcohort) is planned after all subjects of Cohort 1 have completed the study (or discontinued earlier). In case the timing of this IDMC analysis coincides with that of one of the scheduled interim analyses, it may be performed as part of that interim analysis. After the review, the IDMC will provide recommendations to the Sponsor Committee.

At any point during the study, the IDMC has the authority to recommend modifications to the study conduct and/or to the safety assessments to the Sponsor Committee to ensure the safety of enrolled subjects. The IDMC can recommend to the Sponsor Committee to halt a dose arm due to safety concerns.

The IDMC will consist of at least one pediatrician, at least one medical expert in infectious diseases, and at least one statistician. The IDMC responsibilities, authorities, and procedures will be documented in the IDMC Charter.

Given the challenges of ensuring study site preparation in time to recruit for an acute seasonal infection like RSV and the delays caused by implementing an amendment during an RSV season, the following changes will be considered based on the results of any formal interim analysis and may be modified by recommendation of the IDMC based on the review of this study and data from other ongoing studies: changes with respect to the time since onset of symptoms and changes with respect to dose selection. If the IDMC determines that subjects with a time since onset of RSV

symptoms of 5 days prior to randomization may not achieve benefit based on interim results, they may recommend that the time of onset of RSV symptoms to the time of randomization is reduced. Furthermore, if the IDMC determines that subjects with a time since onset of RSV symptoms longer than 5 days prior to randomization may achieve benefit, this duration may be increased to up to 7 days (ie, 7 days from symptom onset to randomization). In addition, the requirement that a minimum of 45% of all enrolled subjects in Cohorts 1 and 2 (ie, maximum 55% of subjects can be enrolled in the >3 days to \leq 5 days stratum) are to have a symptom onset of \leq 3 days before randomization, might be modified based on the recommendation of the IDMC after review of the interim data. Also, in case the data shows no viral and clinical benefit on the low dose, the IDMC might recommend to drop the low dose and continue with a 2:1 randomization for high dose versus placebo. If such modifications are recommended by the IDMC and endorsed by the Sponsor Committee, these changes will be communicated in writing to investigators, health authorities, and IEC/IRB and may be implemented without amendment to this protocol. Details are provided in the IDMC Charter.

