Study participants will be identified when they are hospitalized or expected to be hospitalized within 24 hours after presentation to the hospital (Cohort 1) or present for medical care as outpatients (Cohort 2) with symptoms of an acute respiratory illness supporting a diagnosis of RSV infection (eg, nasal congestion, rhinorrhea, pharyngitis, increased respiratory effort, abnormal breathing sounds [wheezing, rales, or rhonchi], cyanosis, cough, apnea, fever, feeding difficulties, dehydration). For newly enrolled subjects in Cohort 2 after Protocol Amendment 6, cough or wheezing should be accompanied by at least one additional LRTI sign/symptom in order to be eligible. In Cohort 1, a subcohort of 6 subjects >2 and ≤ 3 years will be included, who will follow in general the same assessment schedule as for all subjects enrolled in Cohort 1, although with a specific PK sampling schedule, assigned at randomization (see [Section 9.4.1](#)). Of note, if the subcohort is fully enrolled, additional subjects >2 and ≤ 3 years of age can be enrolled in Cohort 1 and will follow all Cohort 1 procedures.

Overall, for both cohorts, the study will include a Screening Period (Day -1 to Day 1), a Treatment Period (Day 1 to Day 8), and a Follow-up Period (Day 9 to Day 28 [± 3]). The total study duration for each subject will be approximately 29 days (Screening included). A diagram of the study design is provided in [Figure 1](#).

Figure 1: Schematic Overview of the Design of Study 53718678RSV2002

^a In case of ongoing adverse event(s)

Note: Age group 1: ≥28 days and <3 months of age; Age group 2: ≥3 months and <6 months; Age group 3: ≥6 months and ≤3 years

Note: Prior to Protocol Amendment 4, the total daily dose was the same but the daily dosing frequency was qd instead of bid.

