5. TREATMENT ALLOCATION AND BLINDING

Treatment Allocation

Procedures for Randomization and Stratification

Central randomization will be implemented in this study. Within each cohort (including the subcohort of Cohort 1), eligible subjects will be randomized 1:1:1 to receive either a low or a high dose of JNJ-53718678, or placebo. Those randomized to a placebo regimen will be subsequently randomized in a 1:1 ratio to receive either low or high volume of placebo. This results in an overall randomization scheme of 2:2:1:1 (low dose JNJ-53718678, high dose JNJ-53718678, low volume placebo, high volume placebo). Randomization will be based on a computer-generated randomization schedule prepared before the study by or under the supervision of the sponsor.

In the subcohort of Cohort 1, next to randomization to treatment group, within each treatment arm (high dose, low dose, placebo), the 6 subjects will be randomized 1:1 to 1 of 2 different PK sampling groups (see Table 4). In Cohort 1, next to randomization to treatment group, the first 12 subjects of each age group (subcohort not included) will be randomized 1:1 to 1 of 2 different PK sampling groups (see Table 4). Once 12 subjects of a particular age group have been randomized to the 2 different PK sampling groups, the investigator can assign the subsequently enrolled subjects to either of the 2 PK sampling groups, but preferably alternating between 2 different PK sampling groups at this site. In Cohort 2, PK samples will be collected as indicated in the [TIME AND EVENTS SCHEDULE](#).

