11.3. Sample Size Determination

11.3.1. Primary Objective: Establish Antiviral Activity

The basis of the sample size calculation is the antiviral results of Study 53718678RSV1005. In that study, the mean difference in RSV viral load AUC from baseline until Day 5 of the placebo group versus active (adjusted for baseline viral load) was estimated as $105 \log_{10}$ copies.hour/mL (corresponding to a 25% reduction) and the standard deviation (SD) on the RSV viral load AUC as $85 \log_{10}$ copies.hour/mL (corresponding to a CV of approximately 20%).

Assuming a more conservative reduction in RSV viral load AUC of 20% compared to placebo, considering a CV of 35% (slightly higher variability than observed in Study 53718678RSV1005), and a 1-sided alpha of 2.5%; the power to conclude a dose-response using the Multiple Comparison Procedure-Modeling (MCP-Mod) procedure under different assumptions for the dose-response relationship (linear, E_{max} , and exponential,) is provided in [Table 5](#). Based on Study 53718678RSV1005 results, no discrimination between the proposed doses is expected (ie, E_{max} dose-response shape was observed).

Table 5: Power (%) to Conclude Dose-response Using MCP-Mod Under Different Assumptions for the Dose-response Relationship

Assumed CV	Assumed dose-response relationship		
	Linear	E_{max}	Exponential
	Cohort 1 + Cohort 2 (N=74 per treatment arm)		
20%	100.0	100.0	100.0
35%	92.3	95.3	96.6
Cohort 2 only (N=50 per treatment arm)			
20%	99.8	100.0	100.0
35%	79.0	84.0	86.9
Cohort 1 only (N=24 per treatment arm)			
20%	91.5	94.7	96.2
35%	47.1	51.2	54.7

If data of both cohorts are combined (N 74 per treatment arm), the power to conclude dose-response is more than 90% for all 3 different assumptions for the dose-response relationship. If data from Cohort 1 cannot be combined with data from Cohort 2 (eg, due to inconsistency [means and/or variability] in viral load data between cohorts per treatment group), the power to conclude a dose-response using the MCP-Mod procedure in Cohort 2 (N 50 per treatment arm) is at least 79%.

The sample size in Cohort 1 only (N \geq 24 per treatment arm) will provide sufficient power (approximately 90%) if the reduction in RSV viral load AUC is at least 20% with a CV which is not higher than observed in Study 53718678RSV1005 (ie, 20%).

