11.4.1. Antiviral Effect

11.4.1.1. Primary Endpoint

The primary objective is to establish antiviral activity of JNJ-53718678. The primary efficacy endpoint is the RSV viral load area under the curve (AUC) from immediately prior to first dose of study drug through Day 5 derived from the RSV viral load as measured by a qRT-PCR assay in nasal swabs. A hybrid methodology that combines aspects of multiple testing with modeling techniques (MCP-Mod) will be used for evaluating dose-response trends and estimating the dose-response relationships. Refer to Section 2.1.

A set of 3 candidate models will be used to cover a suitable range of possible dose-response shapes (linear, E_{max} , exponential) (see [Figure 3](#)). Doses of the different age groups will be pooled and transformed to the total daily dose of the oldest age group: low dose (3 mg/kg), high dose (9 mg/kg), and placebo (0 mg/kg) and these will be used for the “treatment groups” in the analysis.

Figure 3: Candidate Models for RSV Viral Load AUC From Baseline Until Day 5

AUC values with corresponding covariance matrix will be determined by modeling the \log_{10} viral load values over time using a restricted maximum likelihood-based repeated measures approach. Analyses will include the fixed, categorical effects of treatment, strata, visit, and treatment-by-visit interaction, as well as the continuous, fixed covariates of baseline \log_{10} viral load and baseline \log_{10} viral load by-visit interaction. An unstructured (co)variance structure will be used to model the within subject errors over time. The Kenward-Roger method will be used to approximate the degrees of freedom.

Each of the dose-response shapes in the candidate set will be tested using the corresponding contrast *t*-test statistic, employing a critical value derived for the maximum of the *t*-test statistics (based on the associated multivariate *t*-distribution) to ensure appropriate multiplicity correction that preserves the Type I error rate. A dose-response trend is established when the maximum of the *t*-test statistics exceeds the critical value.

Details will be provided in the SAP that will be finalized before the first formal interim analysis.

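### If the low dose is dropped and allocation changes to 2:1, the stated primary model has no allocation-stage term, so the one-sided 2.5% level is not guaranteed under a residual time trend

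*Protocol*

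**What the plan says.** - **Allocation at the start (section 5).** Within each cohort, "eligible subjects will be randomized 1:1:1 to receive either a low or a high dose of JNJ-53718678, or placebo".
- **Permitted change (section 11.12).** The condition is "in case the data shows no viral and clinical benefit on the low dose", with no numerical rule. The consequence is that the IDMC might recommend to "drop the low dose and continue with a 2:1 randomization for high dose versus placebo". Once the Sponsor Committee endorses it, the change is notified in writing and needs no amendment.
- **Primary model (section 11.4.1.1).** "Analyses will include the fixed, categorical effects of treatment, strata, visit, and treatment-by-visit interaction", plus baseline log10 viral load and its by-visit interaction. The fitted AUC values feed an MCP-Mod test, which takes the largest of three contrast statistics (linear, Emax, exponential).
- **Strata (section 5).** Symptom onset and presence of a risk factor, applied within each cohort. Neither is calendar time.
- **Change of population within Cohort 2 (section 3.1).** "For newly enrolled subjects in Cohort 2 after Protocol Amendment 6, cough or wheezing should be accompanied by at least one additional LRTI sign/symptom".

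The protocol does not say how data from before and after a change of ratio would be combined.

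**The concern.** When the ratio of two arms changes during a trial, the arm that gains has a larger share of late entrants. A simple pooled comparison then carries part of any difference between early and late children as if it were a treatment effect. The low-dose arm adds a second imbalance. It would have no late entrants, yet it enters every MCP-Mod contrast.

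A cohort term would not remove this. The log for Amendment 4 reports that Cohort 1 enrolment is complete, and the remaining scheduled interim analyses (3 and 4) are triggered by Cohort 2 numbers. A switch would therefore fall inside Cohort 2. Recruitment follows RSV seasons, and these interim analyses are preferably held at the end of one, so a switch would tend to separate seasons.

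At stake is whether the stated 2.5% level and the estimated effect of the high dose can be relied on after an adaptation that the protocol itself authorises.

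**Working it through.** **Inputs.** One-sided alpha 2.5% and CV 35% (section 11.3.1). Effect: "Assuming a more conservative reduction in RSV viral load AUC of 20% compared to placebo", which is 0.20/0.35 = 0.571 SD. Planned numbers are 144 in Cohort 1 and 150 in Cohort 2, with a maximum of 300 in Cohort 2. Interim analysis 3 comes at 70 to 80 children in Cohort 2; 75 is used here as the switch point.

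**Assumptions.** The documents give no drift. The range taken is -0.5 to +0.5 residual SD, where + means that later children have lower viral load AUC for given strata and baseline viral load. At CV 35%, 0.5 SD is 17.5% of the mean AUC. The MCP-Mod shape parameters stand in a figure that is not shown, so the low dose is assumed to reach 0.90 (Emax) and 0.02 (exponential) of the maximum effect; linear is 1/3.

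**Step 1: the plan's own figure.** Table 5 gives power of 92.3 / 95.3 / 96.6% (linear / Emax / exponential) for 74 per arm at CV 35%. With the assumed shapes, simulation gives 92.5 / 95.1 / 96.4%, with a critical value of about 2.23. The set-up reproduces the plan.

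**Step 2: shares of late entrants, both cohorts.** Before the switch: 144 + 75 = 219, or 73 per arm. After it: 75 at 2:1, or 50 high and 25 placebo.
- Placebo: 25/98 = 25.5% late
- High: 50/123 = 40.7% late
- Low: 0/73 = 0% late

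**Step 3: high dose versus placebo alone.** Bias = (0.407 - 0.255) x drift, which is 0.151 x drift before rounding. SE = sqrt(1/98 + 1/123) = 0.135 SD. Unmodelled drift also widens the residual SD slightly. The mean of share x (1 - share) over the two arms is 0.2185, so the factor is sqrt(1 + 0.2185 x drift²).

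At +0.5 SD: bias 0.0757 SD, bias/SE = 0.559, threshold 1.96 x 1.027 = 2.013, and error = 1 - Phi(2.013 - 0.559) = 7.3%. The same formula gives 4.5% at +0.25, 2.5% at 0, 1.2% at -0.25 and 0.5% at -0.5.

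**Step 4: why the MCP-Mod test moves further.** At +0.5 SD with no drug effect, the pooled arms show apparent gains of 0.128 (placebo), 0 (low) and 0.203 (high) SD. The exponential contrast sets the high dose roughly against the other two, whose mean is 0.128 x 98/171 = 0.073. The difference is 0.130 SD with SE sqrt(1/171 + 1/123) = 0.118, a shift of 1.10. Over all three arms the widening factor is about 1.02, so the error from this contrast is about 1 - Phi(2.23 x 1.02 - 1.10) = 12%. Simulation of the full maximum test gives 13.0%.

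**Step 5: simulated MCP-Mod error, both cohorts, switch at interim analysis 3.**

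| Residual drift (SD) | Always dropped | Dropped only if low no better than placebo | With additive stage term |
|---|---|---|---|
| -0.5 | 1.0% | 1.6% | 2.4 to 2.6% |
| -0.25 | 1.4% | 1.9% | 2.4 to 2.6% |
| 0 | 2.5% | 2.5% | 2.4 to 2.6% |
| +0.25 | 5.7% | 4.1% | 2.4 to 2.6% |
| +0.5 | 13.0% | 7.8% | 2.4 to 2.6% |

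With Cohort 2 extended to 300 and the low dose always dropped, +0.25 and +0.5 SD give 9.9% and 31%, and -0.5 SD gives 0.8%. If allocation stays 1:1:1, the error is 2.1 to 2.5% over the same drifts. The exposure comes from the change of ratio and the closed arm, not from drift alone.

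**Step 6: cost of the stage term.** For high versus placebo the within-stage information is 1/(1/73 + 1/73) + 1/(1/25 + 1/50) = 36.5 + 16.7 = 53.2. The SE is then 0.1371, against 0.1354 unadjusted, a ratio of 1.013. In Cohort 2 alone (25 v 25, then 50 high v 25 placebo) the ratio is 1.014.

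**The case against.** **The error does not simply rise.** A reader might infer that the switch pushes the error above 2.5% as such. The documents do not support that. With no residual trend it stays at about 2.5%, even when the drop is driven by the data, and with the opposite trend it falls. The one dated population shift in Cohort 2 is Amendment 6, which aims at more severe disease, and the Introduction describes viral load and severity as closely correlated, with one study disagreeing. That would, if anything, suggest higher AUC later, hence bias against the drug. Section 11.12 also allows the symptom window to widen to 7 days, which could work the other way. The direction is open. This objection stands and limits the claim.

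**Only residual drift counts.** Strata and baseline viral load absorb part of any trend. A residual drift of 0.5 SD is nearly as large as the planned effect of 0.571 SD, so the outer rows of the table are severe cases. This stands too.

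**Clinical endpoints.** A reader might extend the point to every clinical comparison. Section 11.4.2 gives the time-to-event models an open list of covariates and fixes no model for the PRESORS scores, so a stage term is not excluded there. The protocol only fails to name it.

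**The SAP and the promised simulations.** Further detail is deferred to an SAP that is not shown, and section 11.1 promises simulated Type I error for the interim decision procedures. An SAP may add the term. But the protocol itself lists the primary model and authorises the change of ratio without amendment, and as written the two do not fit together.

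**The option is unlikely.** It is discretionary, and section 11.3.1 expects no discrimination between the doses. That lowers the priority; the remedy takes effect only if the option is used.

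**Conclusion.** The point holds in a conditional form. If the low dose is dropped and allocation moves to 2:1, an analysis by the stated primary model no longer guarantees the one-sided 2.5% level. The error depends on a time trend that the documents neither quantify nor sign. Over assumed residual drifts of -0.5 to +0.5 SD it ranges from 1.0% to 13.0% if the low dose is always dropped, and from 1.6% to 7.8% if it is dropped only when no better than placebo. The figures assume the planned enrolment, a switch at interim analysis 3, a single step in time and the assumed MCP-Mod shapes. An additive stage term restores the level in every case examined. This is worth correcting because the gap lies between two provisions of the protocol and closing it costs little. It is not evidence that the trial will reach a false positive.

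**What to change.** Add to sections 11.4.1.1 and 11.12: *If the allocation ratio changes, the primary model includes a fixed factor for allocation stage (before/after the change) and its by-visit interaction; low-dose subjects contribute to the first stage only.* In section 11.4.2, name allocation stage among the covariates of the clinical course models.

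The cost is one factor and its interaction, used only if the switch happens, and a standard error for high dose versus placebo that is about 1% larger. Sample size, visits and the MCP-Mod procedure stay as they are.
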